9.1 Protocol amendments

Any amendment to this protocol must be agreed to by the Principal Investigator and reviewed and approved by Celgene. Amendments should only be submitted to IRB/Ethics Committee (EC) after consideration of Celgene review. Written verification of IRB/EC approval will be obtained before any amendment is implemented.

10 Data Management

10.1 Analyses and Reporting

Data will be analyzed and reported after the maximum tolerated dose has been defined, and data regarding the safety and toxicity profile of the drug is available. All subsequent data collected will be analyzed and reported in a follow-up clinical report.

10.2 Data Monitoring Committee

The Data Monitoring Committee (DMC) will be composed of medical and statistical independent reviewers and will meet to review the efficacy and safety data and determine a risk/benefit analysis in this subject population. The purpose of the DMC is to advise on serious safety considerations, lack of efficacy and any other considerations within the charge to the Committee. The DMC may request additional meetings or safety reports as deemed necessary upon discussion with Celgene and its representatives. The DMC may stop the study following review of results from each interim analysis. Appropriate efficacy and safety data summaries will be provided to the DMC for the final analysis.

10.3 Study monitoring and auditing

10.3.1 Investigator responsibilities

Investigator responsibilities are set out in the ICH guideline for Good Clinical Practice (GCP) and in the US Code of Federal Regulations.

Investigators must enter study data onto UTMDACC's protocol data management system (PDMS). The Investigator will permit study-related monitoring visits and audits by the UTMDACC IND Office, Celgene or its representatives, IRB/EC review, and regulatory inspection(s) (e.g., FDA, EMEA, TPP), providing direct access to the facilities where the study took place, to source documents, to CRFs, and to all other study documents.

The Investigator, or a designated member of the Investigator's staff, must be available at some time during monitoring visits to review data and resolve any queries and to allow direct access to the subject's records (e.g., medical records, office charts, hospital charts, and study related charts) for source data verification. The data collection must be

completed prior to each visit and be made available to the UTMDACC IND Office and the Celgene representative so that the accuracy and completeness may be checked.

11 Biostatistical Analysis

11.1 Overview

This is a Phase I study of single agent pomalidomide in patients with symptomatic Waldenström macroglobulinemia whose disease has relapsed and/or is refractory to at least one prior line of therapy.

The objectives of this phase I study are to assess the safety profile of pomalidomide in patients with relapsed Waldenström macroglobulinemia and to determine the maximum tolerated dose (MTD) of pomalidomide in this patient population.

There are four predefined dose levels (1, 2, 3, and 4) for pomalidomide. The study also includes two alternative dosing schedules (A and B). With schedule A, patients will be treated with the study drug for 28 days within each cycle. If the MTD is exceeded at dose level 1 of Schedule A, Schedule B will be explored. With schedule B, patients will be treated for 21 days within each cycle.

Non-hematologic dose limiting toxicity (DLT) is defined as any grade ≥ 3 non-hematological toxicity occurring during the first cycle (28 days on dosing schedule A and 21 days on dosing schedule B) of treatment, with the specific exception of:

- Isolated Grade 3 elevation of liver function tests (LFTs) without associated clinical symptoms, lasting for ≤ 7 days in duration.
- Isolated Grade 3 elevation of amylase without associated clinical symptoms
- Grade 3 hypocalcemia, hypokalemia, hypomagnesemia, hyponatremia, or hypophosphatemia which responds to medical intervention.

Hematological dose limiting toxicity is defined as Grade ≥ 4 neutropenia lasting for ≥ 7 days in duration, any Grade 4 anemia or thrombocytopenia, or any Grade 5 hematologic toxicity occurring during the first cycle (28 days on dosing schedule A and 21 days on dosing schedule B) of treatment.

The standard “3+3” design is applied with 4 pre-defined dose levels. The first cohort of 3 patients will be treated at dose level 1 with schedule A (28-day dosing). If no DLT is observed then the next cohort of 3 patients will be treated at next higher dose level. If one DLT is observed then 3 more patients will be treated at the same dose level. At anytime if 2 or more DLTs are observed within 3 or 6 patients at dose level 1, then schedule A is considered too toxic and will be abandoned. The trial will then be restarted at dose level 1 using dosing schedule B (21-day dosing) to determine the MTD. If dose level 1 with schedule A is well tolerated (less than 2 DLT), then the MTD will be determined with dosing schedule A, and dosing schedule B will not be used. The purpose of schedule B is to prepare for the scenario that dosing schedule A is not tolerable.

	Dosing Schedule A	Dosing Schedule B
Dose level 1	1 mg orally on days 1-28	1 mg orally on days 1-21
Dose level 2	2 mg orally on days 1-28	2 mg orally on days 1-21
Dose level 3	3 mg orally on days 1-28	3 mg orally on days 1-21
Dose level 4	4 mg orally on days 1-28	4 mg orally on days 1-21

The “3+3” algorithm is as follows: (1) If 0 out of 3 patients experiences DLT at the end of first cycle, the next cohort of 3 patients will be treated at the next higher dose level. (2) If 1 out of 3 patients develop a DLT, an additional 3 patients will be treated at the same dose level. If no more DLTs develop at this dose, i.e. 1 out of a total of 6 patients develops a DLT, the dose escalation will continue for the next cohort of 3 patients. (3) At any given dose, if more than 1 out 3 patients or 1 out of 6 patients experience DLT, the dose level exceeds the MTD and 3 more patients will be treated at the next lower dose if there are less than 6 patients already treated at that dose. Following the above scheme, MTD is defined as the highest dose level in which 6 patients have been treated with less than 2 instances of DLT.

Analysis Plan

Toxicity data will be summarized using frequency tables. The types and severity of toxicity will be evaluated.

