6.4 Drug Administration

6.4.1 Treatment assignments

This is a Phase I non-randomized study. Eligible patients will be allocated to treatment in the order in which they sign the informed consent and that all documentation needed to confirm eligibility has been completed. A maximum of 30 subjects will be enrolled and treated with single agent pomalidomide. Starting at dose level 1 in Schedule A, the study will enroll patients in cohorts of 3, following a standard 3 +3 statistical design. (see Section 11.0).

Definition of Dose Limiting Toxicity (DLT):

Toxicity will be evaluated according to the NCI CTCAE version 4.0, (see Appendix E)

1) Non-hematologic dose limiting toxicity (DLT) is defined as any grade ≥ 3 non-hematological toxicity occurring during the first 28 days (first cycle) of treatment, with the specific exception of:

- Isolated Grade 3 elevation of liver function tests (LFTs) without associated clinical symptoms, lasting for ≤ 7 days in duration.
- Isolated Grade 3 elevation of amylase without associated clinical symptoms
- Grade 3 hypocalcemia, hypokalemia, hypomagnesemia, hyponatremia, or hypophosphatemia which responds to medical intervention.

2) Hematological dose limiting toxicity is defined as Grade ≥ 3 neutropenia with fever ≥ 38.5 , Grade 4 neutropenia lasting for ≥ 7 days in duration, or any Grade 4 anemia or thrombocytopenia occurring during the first 28 days (first cycle) of treatment.

Definition of Maximum Tolerated Dose (MTD): MTD is defined as the highest dose level in which 6 patients have been treated with less than 2 instances of DLT.

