6.4.2 Dosing regimen

There are four predefined dose levels (1, 2, 3, and 4) for pomalidomide, and two alternative dosing schedules (A and B). With schedule A, patients will be treated with the study drug for 28 days within each cycle. With schedule B, patients will be treated for 21 days within each 28 day cycle. Schedule B will only be explored if the MTD is exceeded at dose level 1 within Schedule A. The first cohort of 3 patients will be treated at dose level 1 with schedule A (28-day dosing). If no dose limiting toxicities (DLTs) are observed then the next cohort of 3 patients will be treated at next higher dose level. If one DLT is observed then 3 more patients will be treated at the same dose level. At anytime if 2 or more DLTs are observed within 3 or 6 patients at dose level 1, then schedule A is considered too toxic and will be abandoned. Patient enrollment will then be resumed using dose level 1 of dosing schedule B (21-day dosing) to determine the MTD. The purpose of schedule B is to prepare for the scenario that dosing schedule A is not tolerable.

Table 1

	Dosing Schedule A	Dosing Schedule B
Dose level 1	1 mg orally on days 1-28	1 mg orally on days 1-21
Dose level 2	2 mg orally on days 1-28	2 mg orally on days 1-21
Dose level 3	3 mg orally on days 1-28	3 mg orally on days 1-21
Dose level 4	4 mg orally on days 1-28	4 mg orally on days 1-21

Dose escalation will continue in 1 mg increments until the MTD is reached. Once the MTD has been determined, an additional 6 patients will be treated at this dose level.

An additional 6 patients will be treated at the MTD.

Dosing will be each night at approximately the same time. Pomalidomide should be taken with a glass of water on an empty stomach. **Only enough pomalidomide for one cycle of therapy will be supplied to the patient each cycle.**

Patients will continue receiving treatment with pomalidomide until disease progression or unacceptable toxicity develops.

Patients are to receive oral aspirin (325mg) as prophylactic anti-thrombotic treatment unless it is contraindicated, or the patient has a platelet count of less than 50,000. If the patient is intolerant of aspirin and has a platelet count of 50,000 or greater, the investigator is to prescribe therapeutic dose warfarin or low molecular weight heparin.

Pomalidomide capsules should be swallowed whole, and should not be broken, chewed or opened. Pomalidomide should be taken without food, at least 2 hours before or 2 hours after a meal.

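### Section 11.1 ends the Schedule B DLT window at Day 21, but Section 6.4.1 counts 28 days for every patient; if Section 11.1 is applied, any bias in the Schedule B MTD is upward

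*Combined protocol and SAP*

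**What the plan says.** The DLT definition appears twice.

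- **Section 6.4.1**, under its own DLT heading, covers "non-hematological toxicity occurring during the first 28 days (first cycle) of treatment". The hematologic criterion carries the same limit, "occurring during the first 28 days (first cycle) of treatment". Neither makes an exception by schedule.
- **Section 11.1** counts both kinds of DLT over the "first cycle (28 days on dosing schedule A and 21 days on dosing schedule B) of treatment".

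On cycle length, Section 6.4.2 states: "With schedule B, patients will be treated for 21 days within each 28 day cycle". The synopsis says the same.

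The window feeds the primary endpoint through the 3+3 algorithm in Section 11.1. Escalation is judged at the close of the first cycle ("If 0 out of 3 patients experiences DLT at the end of first cycle"), and the "MTD is defined as the highest dose level in which 6 patients have been treated with less than 2 instances of DLT". Schedule B is a contingency: "If the MTD is exceeded at dose level 1 of Schedule A, Schedule B will be explored".

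**The concern.** Section 11.1 appears to take the Schedule B dosing period for the cycle. The two definitions then classify the same patient differently. A Schedule B patient whose Grade 4 thrombocytopenia first appears on Day 24 has a DLT under Section 6.4.1 and none under Section 11.1. In cohorts of three, one event can decide whether the dose goes up.

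Neither text can be set aside as secondary. Section 6.4.1 holds the headed definition, while Sections 6.1 and 6.4.1 both send the reader to Section 11 for the 3+3 design. The cohort decision point on Schedule B is Day 21 or Day 28 depending on the section followed. Section 11.2 also ties inclusion in the MTD determination to completing one cycle, so the length of that cycle affects who is counted.

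Schedule B opens only after the lowest Schedule A dose has produced two or more DLTs, so an undercount would come when tolerability is already in doubt.

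**Working it through.** **The plan's own figure.** Section 11.6 gives up to 30 patients for dose finding. Six at Schedule A level 1 plus four Schedule B levels of six is 6 + 4 × 6 = 30, which reproduces it. This figure does not depend on the DLT window. The plan gives no DLT rate, error rate or power that bears on the window.

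**Days at issue.** 28 − 21 = 7 days, or 7/28 = 25% of the Schedule B cycle.

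**Direction.** The 21-day window counts a subset of the events in the 28-day window. It can only lower the DLT count, so it can only make a level easier to clear.

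**Size for one level.** Let p be the true 28-day DLT probability and f the share of DLTs that first qualify on Days 22 to 28. The documents give neither, so both are assumed and varied. The probability counted in 21 days is q = p(1 − f). A level clears with 0 of 3 DLTs, or with 1 of 3 followed by 0 of 3:

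P(clear) = (1 − q)³ + 3q(1 − q)² × (1 − q)³ = (1 − q)³ + 3q(1 − q)⁵

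With p = 0.33:

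- 28-day window, q = 0.33: 0.301 + 0.134 = 0.434.
- 21-day window, f = 0.25, q = 0.2475: 0.426 + 0.179 = 0.605.

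A constant daily hazard is another timing assumption: q = 1 − (1 − p)^(21/28). At p = 0.33, q = 0.259 and P(clear) = 0.579.

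| True 28-day rate | 28-day window | 21-day, f = 0.10 | 21-day, f = 0.25 | 21-day, f = 0.40 | 21-day, constant hazard |
|---|---|---|---|---|---|
| 33% | 0.434 | 0.500 | 0.605 | 0.713 | 0.579 |
| 40% | 0.309 | 0.378 | 0.494 | 0.622 | 0.457 |
| 50% | 0.172 | 0.234 | 0.351 | 0.494 | 0.301 |

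**Size for the declared MTD.** Clearing one level is not the same as setting the MTD too high, so the whole 3+3 was enumerated exactly. This included stepping down and adding three patients where a level had only three, until six were treated with fewer than two DLTs. The table gives the chance that the declared MTD is a level whose true 28-day DLT rate exceeds 33%, given that Schedule B is in use.

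| Assumed true rates, levels 1 to 4 | 28-day window | f = 0.10 | f = 0.25 | f = 0.40 |
|---|---|---|---|---|
| 10/20/33/50% | 3.1% | 5.7% | 12.7% | 25.1% |
| 20/33/45/60% | 5.1% | 8.7% | 17.5% | 31.6% |

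**Chance that Schedule B opens.** This is 1 − P(clear) at Schedule A level 1. If the true rate there is 10%, it is 1 − (0.729 + 0.177) = 9%. If it is 20%, it is 1 − 0.709 = 29%. Both rates are assumed.

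**Neutropenia with a duration.** Section 11.1 counts Grade 4 "neutropenia lasting for ≥ 7 days in duration". If all seven days must fall inside the window, the latest qualifying onset is Day 21 − 7 + 1 = 15, against Day 28 − 7 + 1 = 22.

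**The case against.** The best defense is that the parenthesis in Section 11.1 is loose wording for dosing days. The same section ties the DLT to the first cycle and judges cohorts when that cycle ends, and elsewhere the Schedule B cycle is 28 days. On that reading the decision already falls on Day 28 and nothing is lost. This is plausible, but the parenthesis appears in both DLT paragraphs and, read literally, sets the cycle length. The ambiguity remains.

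Other limits stand:

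- The issue arises only if Schedule B opens and Section 11.1 is the text applied.
- Days 22 to 28 are off drug on Schedule B. The documents give no data on onset within the cycle, and if few DLTs first qualify then, the effect is small.
- A reader might infer that late toxicity goes unseen. It does not: Sections 11.2 and 11.3 put every treated patient in the safety analysis, and six more patients are treated at the MTD.
- The Day 15 limit for neutropenia is not fixed by the text. An episode that starts inside the window and runs past its end could equally be counted.
- A reader might infer that Schedule B is made to look safer than Schedule A. No decision rule compares the two; Schedule A is abandoned before Schedule B begins.
- A reader might add that blood counts reach their low point late in the cycle, which would enlarge the effect. The documents do not say so.

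**Conclusion.** The inconsistency is real and sits in the definition behind the primary endpoint. Under Section 11.1 as written, the Schedule B DLT count can be lower than under Section 6.4.1 and never higher, so the direction of any bias in the MTD is settled. The size is not. At a true 28-day rate of 33%, the rise from 43% in the chance of clearing runs from a modest one (to 50%) to a large one (to 71%), according to the assumed share of DLTs in the last week. Constant hazard (58%) is one point in that range and should not be read as the expected effect.

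The documents do not support the stronger claim that the Schedule B MTD will be set too high. That would require Schedule B to open, Section 11.1 to be followed, and enough DLTs to first qualify on Days 22 to 28.

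**What to change.** Reconcile Sections 6.4.1 and 11.1 to one DLT window, stated identically in both, before any Schedule B cohort is assessed. Deleting the parenthesis from both DLT paragraphs of Section 11.1 would bring it into line with Section 6.4.1, with the 28-day cycle in the synopsis and Section 6.4.2, and with its own end-of-cycle decision point. If a 21-day window was intended, the sponsor should justify it and amend Section 6.4.1. In either case the plan should say whether a neutropenia episode must complete its seven days inside the window.

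The cost of deleting the parenthesis is one wording change and at most 7 days per Schedule B cohort decision. With up to 24 Schedule B patients in groups of three, that is 8 decisions and at most 8 × 7 = 56 days, or none if Day 28 was always meant. The 30-patient maximum for dose finding does not change.

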4.2 POMALIDOMIDE

Pomalidomide is an IMiD analogue of thalidomide that, among other anti-tumor properties, on an equimolar basis *in vitro*, displays equivalent anti-angiogenic activity, about 8-fold greater activity in stimulation of apoptosis, at least 10-fold greater activity in inhibition of cellular COX-2 production and over 4,000-fold greater activity in inhibition of cellular TNF-alpha production relative to thalidomide.^{20,21} Pomalidomide has also been shown to stimulate antibody-dependent cytotoxic T-cell activity (ADCC).²⁰

At tolerated doses (MTD = 2 mg QD and 5 mg QOD), pomalidomide has been shown to be active in subjects with relapsed or refractory multiple myeloma (MM).^{20,22,23} In 45 subjects who received doses of pomalidomide ranging, by cohort, up to 10 mg daily, the most commonly occurring dose-limiting toxicity (DLT) was reversible neutropenia. As with other IMiDs administered to subjects receiving concomitant systemic steroids, deep vein thrombosis (DVT) was seen (in 1 subject each in this study and in its subsequent named patient supply rollover program).^{20,24}

Recently, efficacy and safety data from a phase II study, by Lacy et al., were published.⁹ Sixty patients with relapsed or refractory multiple myeloma were enrolled. Pomalidomide was given orally at a dose of 2 mg daily on days 1-28 of a 28-day cycle and dexamethasone was given orally at a dose of 40 mg daily on days 1, 8, 15, 22 of each cycle. Patients also received aspirin 325 mg once daily for thromboprophylaxis. The study endpoints were the response rate in patients taking pomalidomide plus dexamethasone including patients with lenalidomide resistant refractory multiple myeloma, and safety of pomalidomide plus dexamethasone. Thirty eight patients achieved objective response (63%) including CR in 3 patients (5%), VGPR in 17 patients (28%), and PR in 18 patients (30%). The CR + VGPR rate was 33%. Grade 3 or 4 hematologic toxicity occurred in 23 patients (38%) and consisted of anemia in three patients (5%), thrombocytopenia in two patients (3%) and neutropenia in 21 (35%). Among those that developed grade 3/4 neutropenia, all first experienced the neutropenia in cycle 1-3; no new patients experienced grade 3/4 neutropenia in cycle 4 or later. The most common non-hematological grade 3/4

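### Sections 6.4.1 and 11.1 define the hematologic DLT differently (febrile Grade 3 or worse neutropenia counts only in 6.4.1), so one cohort can both fail and pass the MTD rule.

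*Combined protocol and SAP*

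**What the plan says.** Section 6.4.1, under its definition of DLT, begins: "Hematological dose limiting toxicity is defined as Grade ≥ 3 neutropenia with fever ≥ 38.5". It then adds Grade 4 neutropenia persisting at least 7 days, and Grade 4 anemia or thrombocytopenia, all within the first 28 days.

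Section 11.1 gives its own definition: "Hematological dose limiting toxicity is defined as Grade ≥ 4 neutropenia lasting for ≥ 7 days in duration, any Grade 4 anemia or thrombocytopenia". It adds any Grade 5 hematologic toxicity. It has no febrile criterion, and it describes the first cycle as 28 days on Schedule A and 21 days on Schedule B.

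The counting rules are shared. Section 6.4.1 states that "MTD is defined as the highest dose level in which 6 patients have been treated with less than 2 instances of DLT", and 11.1 repeats this. Section 11.1 also says that "if more than 1 out 3 patients or 1 out of 6 patients experience DLT, the dose level exceeds the MTD". After one DLT in three and none in the next three, "1 out of a total of 6 patients develops a DLT, the dose escalation will continue for the next cohort of 3 patients". With two or more DLTs at dose level 1, "then schedule A is considered too toxic and will be abandoned".

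Sections 6.1 and 6.4.1 refer to Section 11.0 for the 3+3 design. Neither DLT definition is given precedence.

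**The concern.** The two definitions disagree on a specific group of patients: those with febrile neutropenia in cycle 1 that is Grade 3, or Grade 4 lasting under 7 days, and with no other DLT. Section 6.4.1 counts them; 11.1 does not. The non-hematologic part of 11.1 does not bring them back, because it covers only non-hematologic toxicity and 6.4.1 itself lists the febrile event as hematologic.

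The DLT count is the only input to escalation, to the MTD and to abandoning Schedule A. One text can therefore declare a dose too toxic while the other allows the next cohort to be treated above it. The count also matters for the individual patient: Section 6.4.5 bars interruptions and reductions in cycle 1 unless a DLT occurs, although it also lets the investigator reduce further or stop for any adverse event.

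The event is foreseeable. Section 4.2 names reversible neutropenia as the commonest DLT in the earlier myeloma study. It also reports Grade 3-4 neutropenia in 21 of 60 myeloma patients given 2 mg daily with dexamethasone.

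Two smaller differences accompany this one. Grade 5 hematologic toxicity is named only in 11.1. The 21 days for Schedule B in 11.1 may mean dosing days, which would fit a decision rule worded as "If 0 out of 3 patients experiences DLT at the end of first cycle". It may instead mean a 21-day window that drops events on days 22-28 of a cycle that Section 6.4.2 makes 28 days long.

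**Working it through.** **The plan's own figure.** Section 11.6 gives up to 30 patients for dose finding. This reproduces as 6 at dose level 1 on Schedule A plus 4 levels × 6 on Schedule B: 6 + 24 = 30. The DLT wording does not change it.

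**Decisions from the text alone.** Let F be a patient counted only by 6.4.1 (febrile, no other DLT) and O a patient with a DLT under both texts. Applying the 11.1 algorithm:

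| Observed | 6.4.1 count and action | 11.1 count and action |
|---|---|---|
| 1 F in 3 | 1/3, add three | 0/3, escalate |
| 1 F + 1 O in 3 | 2/3, exceeds MTD | 1/3, add three |
| 2 F in 3 | 2/3, exceeds MTD | 0/3, escalate |
| 1 F + 1 O in 6 | 2/6, exceeds MTD | 1/6, escalate or candidate MTD |

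At dose level 1, the last three rows abandon Schedule A under 6.4.1 only. No rate is assumed here.

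**Second row continued.** Under 11.1 the three added patients are all free of DLT with probability (1−p)³. At assumed p = 10%, 20% and 30% this is 0.9³ = 0.729, 0.8³ = 0.512 and 0.7³ = 0.343. Under 6.4.1 the dose has already failed.

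**One dose.** The chance that a dose passes is (1−p)³ + 3p(1−p)⁵. Assume a DLT rate of 20% under 11.1, and that 6.4.1 adds 1, 2 or 5 percentage points:

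- p = 0.20: 0.512 + 0.6 × 0.3277 = 0.709
- p = 0.21: 0.687
- p = 0.22: 0.665
- p = 0.25: 0.600

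For scale, 21/60 = 0.35, so 1 to 5 points correspond to 0.01/0.35 = 3% up to 0.05/0.35 = 14% of patients with Grade 3-4 neutropenia. That 35% comes from myeloma patients on dexamethasone, with first onset anywhere in cycles 1-3.

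**Whole Schedule A escalation.** A paired 3+3 simulation used 400,000 trials per set of base rates and six potential patients per level. Each patient was scored at p for 11.1 and at p plus the extra for 6.4.1 from the same random draw, and the MTD required six treated with fewer than two DLTs. The table gives the percentage of trials in which the Schedule A result (MTD level, or no MTD) differs, for 1 / 2 / 5 extra points:

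| Extra DLTs occur at | Base 10/20/30/40% | Base 5/10/15/20% |
|---|---|---|
| 3-4 mg | 1.8 / 3.6 / 8.2 | 3.6 / 7.1 / 17.2 |
| 2-4 mg | 3.9 / 7.6 / 17.6 | 5.2 / 10.4 / 24.8 |
| all doses | 5.6 / 11.0 / 25.6 | 6.3 / 12.5 / 30.0 |

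Section 6.1.1.3 ties the neutropenic DLTs to higher doses, which favours the 3-4 mg row. The simulation treats 6.4.1 as the broader text, so the direction of the difference is assumed.

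**The case against.** The strongest reply is that 6.4.1 carries the labelled definition in the operational section, while 11.1 is headed as an overview. The references to Section 11.0 concern the design, so a reader might let 6.4.1 define the event and Section 11 supply the counting rule. That is a reasonable inference, but no text states it, and 11.1 sets out a complete definition of its own rather than an abbreviated pointer.

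The discordant group is also narrow. Any accompanying Grade 3 or worse non-hematologic event, outside the listed exceptions, counts under both texts. The example shows that divergence is possible, not that it is likely. This stands.

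The objection to the numbers also stands in large part. Base rates, extra points and dose pattern are all assumed, and the results spread from 2% to 30%. The 35% used for scale was seen at 2 mg, whereas the favoured row has no extra events at 2 mg. Neutropenia at 1 and 2 mg is described as lower grade, so the dose-level-1 consequence is the least supported. The simulation stops at the Schedule A result and does not estimate how often the trial's final MTD would change. The conclusion therefore should not rest on these figures.

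The Grade 5 and Schedule B points are minor: a hematologic death would hardly go uncounted in practice, and 6.4.1 already states 28 days. Expedited SAE reporting and the data monitoring committee give some protection to patients, but neither settles the DLT count.

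**Conclusion.** The concern holds and should be fixed before any escalation decision depends on it. Two current definitions of the event that sets the primary endpoint conflict, and identical data can give 2/3 under one and 1/3 or 0/3 under the other. That follows from the text and needs no assumed rate.

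How often it would matter is unknown, because the documents give no febrile neutropenia rate. On the assumptions shown, the effect on the Schedule A result ranges from about 2% of trials (1 extra point, 3-4 mg only, higher base rates) to 30% (5 extra points, all doses, lower base rates). No size is claimed for the Grade 5 or Schedule B wording.

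**What to change.** Keep a single definition in Section 6.4.1 and replace the one in 11.1 with a cross-reference. The hematologic DLT should comprise:

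- Grade 3 or worse neutropenia with fever of 38.5 or above
- Grade 4 neutropenia persisting 7 days or more
- Grade 4 anemia or Grade 4 thrombocytopenia
- any Grade 5 hematologic event

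Keep the non-hematologic criteria and exceptions as they are, and apply a 28-day window on both schedules. Until the amendment is approved, count an event as a DLT for every escalation decision if either section does.

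The cost is one wording amendment, with the planned maximum staying at 30. The declared MTD may be lower than under 11.1 alone. If febrile episodes also occur at 1 mg, Schedule A is abandoned at level 1 somewhat more often: at an assumed 10% base, one minus the pass probability rises from 9.4% to 11.1%, 12.9% or 18.6% with 1, 2 or 5 extra points. Schedule B cohorts may be observed up to 28 − 21 = 7 days longer than under the 21-day reading.
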